2.4.4.2 Analyses of secondary efficacy endpoints

For continuous secondary efficacy parameters (see [Section 2.1.3](#)) with missing data at baseline, missing data will be imputed using MI under the missing at random (MAR) assumption. Missing data at baseline will be imputed using regression method that includes randomization stratum of HbA1c ($\leq 8.5\%$, $> 8.5\%$), randomization stratum of SBP (< 130 , ≥ 130 mmHg), and baseline value in the imputation model (see sample code Part 1 or 2b in [Appendix A](#)).

Each continuous secondary endpoints (see [Section 2.1.3](#)) will be analyzed using a similar ANCOVA model including the measurements at baseline and endpoint (observed or imputed). The missing data at endpoint will be imputed by the retrieved dropouts & washout imputation method or by the control-based copy reference imputation method according to the criterion described in [Section 2.4.4.1](#). After the imputation, each of the complete datasets will be analyzed by an ANCOVA model.

The ANCOVA model with treatment groups (sotagliflozin 400 mg, sotagliflozin 200 mg, placebo), randomization stratum of HbA1c ($\leq 8.5\%$, $> 8.5\%$), randomization stratum of SBP (< 130 , ≥ 130 mmHg), and country as fixed effects, and baseline secondary endpoint value as a covariate. For the analysis of SBP in patients with baseline SBP ≥ 130 mmHg, the randomization stratum of SBP will not be included in the ANCOVA model. Results from each complete dataset will be combined using Rubin's rule to provide the adjusted mean change from baseline to Week 26 (or Week 12 for SBP) for each treatment group, as well as the between-group difference (comparing sotagliflozin 400 mg, sotagliflozin 200 mg vs placebo) and the 95% CI for the difference.

UACR will be log-transformed at patient level before analysis, and geometric means (with and without ANCOVA model adjustment), differences between treatments and 95% CIs will be back-transformed to original scale. Summary statistics of UACR in log scale will then be calculated for

each treatment group at each visit and back-transformed to provide the geometric mean and its associated percent change of UACR from baseline.

For all continuous secondary endpoints, summary statistics at scheduled visits will be provided for each treatment group. The summary will include the number of observations, mean, SD, SE, minimum, median, and maximum. Graphical presentations will also be used to examine trends over time using mean values (\pm SE) and mean changes from baseline (\pm SE) at each of the scheduled visits. In addition, SBP will be summarized descriptively at each visit for those with baseline SBP \geq 140 mmHg.

The categorical secondary efficacy of HbA1c ($<$ 6.5%, $<$ 7% at Week 26 respectively) will be analyzed using a Cochran-Mantel-Haenszel (CMH) method stratified by randomization stratum of HbA1c (\leq 8.5%, $>$ 8.5%), and randomization stratum of SBP ($<$ 130, \geq 130 mmHg). The proportion in each treatment group, as well as the difference of proportions between sotagliflozin and placebo with associated 2-sided 95% CI will be provided. For HbA1c responders at Week 26 ($<$ 6.5%, $<$ 7% respectively), all values at Week 26 will be used to determine whether a patient is a responder or not, even if they are measured after IMP discontinuation or rescue medication use. Patients who have no HbA1c measurement at Week 26 will be treated as non-responders. Summary tables and graphs will also be provided by treatment group at scheduled visits.

For between-group comparison, a sensitivity analysis will be performed respectively for HbA1c $<$ 6.5% responder analysis by excluding patients whose HbA1c values at baseline are $<$ 6.5%, and for HbA1c $<$ 7% responder analysis by excluding patients whose HbA1c values at baseline are $<$ 7% using the same CMH test mentioned above. Similarly, by-visit summary may also be provided excluding those patients.

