1 OVERVIEW AND INVESTIGATIONAL PLAN

1.1 STUDY DESIGN AND RANDOMIZATION

This is a Phase 3, multicenter and multinational, double-blind (single-blind Run-in Phase), placebo-controlled, parallel-group study. Patients were randomly assigned 1:1:1 to the following 3 treatment groups.

- Sotagliflozin 400 mg
- Sotagliflozin 200 mg
- Placebo

All patients will have a Screening Period comprised of an up to 2-week Screening Phase and a 2-week, single-blind placebo Run-in Phase prior to randomization. Following randomization, patients will have a 26-week, double-blind Treatment Period, 26-week, double-blind Extension Period, and a 4-week post-treatment Follow-up period (patients who prematurely discontinue the study treatment are expected to continue in the study).

At the end of the screening period, eligible patients will be centrally randomized (using permuted block randomization schedule) via an Interactive Response Technology (IRT).

The randomization will be stratified by:

- Hemoglobin A1c (HbA1c) at the screening ($\leq 8.5\%$ and $> 8.5\%$)
- Mean systolic blood pressure (SBP) at the screening visit (< 130 mmHg, ≥ 130 mmHg).

It is anticipated to randomize a total of approximately 276 patients.

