1.3 DETERMINATION OF SAMPLE SIZE

The sample size/power calculations were performed based on the primary endpoint. Assuming a common standard deviation of 1.2% and using a 2-sided test at a 0.05 α -level, 92 patients in each group will provide 80% power to detect a treatment difference of 0.5% in mean HbA1c change from Baseline to Week 26 between sotagliflozin 400 mg and placebo.

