2.1.3.2 Secondary efficacy endpoints

The secondary efficacy endpoints are:

- Change from Baseline to Week 26 in HbA1c (%) comparing sotagliflozin 200 mg versus placebo
- Comparison sotagliflozin 400 mg and 200 mg, respectively, versus placebo for:
 - Change from Baseline in FPG at Week 26

- Change from Baseline in body weight at Week 26
- Change from Baseline in SBP at Week 12 for patients with baseline SBP ≥ 130 mmHg
- Change from Baseline in SBP at Week 12 for all patients
- Change in the UACR (%) from Baseline to Week 26 for patients with a UACR >30 mg/g at baseline
- Proportion of patients with HbA1c $<6.5\%$, $<7.0\%$ at Week 26.

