Appendix A Sample SAS® code for analyses of efficacy endpoints

```

* VARIABLES;
* ptid - patient identification;
* treat - treatment;
* strata1 - stratification factor 1;
* strata2 - stratification factor 2;
* value0 - value at baseline;
* value1 ... valuen - value at each post-baseline visit for a total of n visits; valuen at the endpoint visit;
* change - change from baseline;

***** Part 1: Preferred imputation method: the retrieved dropouts and washout imputation *****,;
*****
*.;

/* Part 1a, for parameters with no missing data at baseline */;

* MI in patients who prematurely discontinued IMP before the endpoint using the endpoint data from its
own group (retrieved dropouts);
proc sort data=ads;
  by treat ptid;
run;

proc mi data=ads out=disc_mi nimpute=2000 seed=97531;
  where discontinue = "Y";
  by treat;
  var value0 valuen;
  monotone regression (valuen = value0 );
run;

* MI in patients who stay on the IMP until the endpoint visit using the endpoint data from the placebo group
(wash-out MI);
proc sort data=ads;
  by ptid;
run;

proc mi data=ads out=comp_mi nimpute=2000 seed=75319;
  where discontinue="N" and (treat=1 or (treat ne 1 and valuen =. )); *1 denotes placebo group;
  class strata1 strata2;
  var strata1 strata2 value0 valuen;
  monotone regression (valuen = strata1 strata2 value0 );
run;

* Repeat dataset with the same number of replications for remaining patients who have complete data at
the endpoint visit;
data comp_trt;

```

Statistical Analysis Plan

Version: Final 3.0

Lexicon Pharmaceuticals Protocol No. EFC15166

Date of Issue: 21 November 2019

Covance Study ID: 000000155203

```
set ads (where=(discontinue="N" and treat ne 1 and valuen ne .));
_imputation_=0;
do i = 1 to 2000;
    _imputation_=_imputation_+1;
    output;
end;
run;
```

* Combine MI from the three subsets of patients;

```
data mi_1;
    set disc_mi comp_mi comp_trt;
run;
```

/*Part 1b, for parameters with missing data at baseline */

* To impute the missing data at baseline;

```
proc sort data=ads;
    by ptid;
run;
```

```
proc mi data=ads out=mi_base nimpute=2000 seed=13579;
    class strata1 strata2;
    var strata1 strata2 value0;
    monotone regression;
run;
```

* MI in patients who prematurely discontinued IMP before the endpoint using the endpoint data from its own group (retrieved dropouts);

```
proc sort data=mi_base;
    by _imputation_ treat ptid;
run;
```

```
proc mi data=mi_base out=disc_mi nimpute=1 seed=97531;

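### Missing secondary-endpoint baselines are drawn from the randomization strata alone, which can cost precision for UACR, and the SAP does not stop an imputed value from placing a patient in the >30 mg/g subset

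*SAP*

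**What the plan says.** SAP 2.4.4.2 deals with continuous secondary parameters that lack a baseline: "missing data will be imputed using MI under the missing at random (MAR) assumption". It then gives the model: "Missing data at baseline will be imputed using regression method that includes randomization stratum of HbA1c", followed by the SBP stratum and the baseline value. The last item is the variable being imputed, so it supplies no information. Appendix A matches. In Parts 1b and 2b, the step that opens "proc mi data=ads out=mi_base nimpute=2000 seed=13579" lists only the two strata and `value0`. Treatment, the endpoint value `valuen` and all intermediate visits are absent.

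The completed baseline is then the ANCOVA covariate, and it is also subtracted to form the change from baseline.

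The secondary UACR endpoint in SAP 2.1.3.2 is "Change in the UACR (%) from Baseline to Week 26 for patients with a UACR" above 30 mg/g at baseline. Neither the text nor the code says whether an imputed baseline can meet that criterion, and Appendix A has no subsetting step. Appendix D lists UACR for all patients as well as for the subset.

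**The concern.** Where it is observed, the Week 26 value is usually a strong predictor of a missing baseline. A draw from the strata alone is unrelated to that patient's outcome, yet the ANCOVA uses it as though it were that patient's baseline. The covariate slope is attenuated, the residual variance for those patients grows, and the draws add between-imputation variance.

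UACR at both doses supplies two of the four Hochberg tests in SAP 2.4.4.4. If both UACR tests fail with p above 0.05, the other two are both declared significant only if the larger of their p-values is at or below 0.05/3 = 0.0167. Otherwise one of them needs p at or below 0.05/4 = 0.0125. Lost precision in UACR can therefore affect other claims. SAP 1.6 also repeats the secondary analyses at Week 52, so the rule is used again there.

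**Working it through.** **1. The plan's own figure.** The only sizing in the SAP is for HbA1c (SAP 1.3): "Assuming a common standard deviation of 1.2% and using a 2-sided test at a 0.05" level, "92 patients in each group will provide 80% power" for a difference of 0.5%. The normal approximation gives n = 2 × (1.960 + 0.842)² × 1.2² / 0.5² = 90.4, so 91 per arm. At 92 per arm, 0.5 / (1.2 × √(2/92)) = 2.826 and Φ(2.826 − 1.960) = 80.7%. The noncentral t gives 80.3%. The figure reproduces. The documents give no figure for UACR or for the number of missing baselines.

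**2. Which endpoints can lack a baseline.** SAP 2.1.1 takes the last available pre-dose value. By the flow chart:

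| Endpoint | Scheduled pre-dose measurements |
|---|---|
| FPG | Visits 1 and 3 |
| Body weight, SBP | Visits 1, 2 and 3 |
| UACR | Week 0 home urine only |

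Only UACR has no scheduled fallback. Footnote p of the flow chart asks for the visit to be rescheduled if urine was missed. The primary HbA1c analysis cites Parts 1a and 2a, the code for parameters with no missing baseline.

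**3. Cost in precision.** Simulation: three arms of 92, 800 trials per setting, 12 imputations, ANCOVA on change with baseline, strata and treatment (country omitted), combined by Rubin's rule. Assumptions not in the documents: unit-SD log scale, true effect −0.30 SD, strata explain 2% of baseline variance, baselines missing completely at random, Week 26 complete. Variance ratio = (SE / SE with full baselines)².

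| Correlation | Missing | Full SE | Strata-only SE (ratio) | With Week 26 and treatment (ratio) | Complete cases (ratio) |
|---|---|---|---|---|---|
| 0.8 | 2% | 0.0889 | 0.0935 (1.11) | 0.0895 (1.01) | 0.0898 (1.02) |
| 0.8 | 5% | 0.0892 | 0.1001 (1.26) | 0.0909 (1.04) | 0.0915 (1.05) |
| 0.8 | 10% | 0.0888 | 0.1082 (1.48) | 0.0921 (1.08) | 0.0937 (1.11) |
| 0.5 | 2% | 0.1285 | 0.1298 (1.02) | 0.1289 (1.01) | 0.1298 (1.02) |
| 0.5 | 5% | 0.1285 | 0.1316 (1.05) | 0.1294 (1.01) | 0.1320 (1.06) |
| 0.5 | 10% | 0.1285 | 0.1344 (1.09) | 0.1305 (1.03) | 0.1356 (1.11) |

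A second simulation at correlation 0.8 (80 per arm, 400 trials, 20 imputations) gave strata-only ratios of 1.105, 1.257 and 1.487.

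In these settings the strata-only estimate averaged −0.29 to −0.31 against the true −0.30, with coverage of 94% to 98%. At 5% missing and correlation 0.8, power was 89.9% with full baselines, 85.0% strata-only, 89.4% with Week 26 and treatment, and 89.5% on complete cases. At correlation 0.8 the stated rule does worse than imputing no baseline at all; at 0.5 it does about as well or slightly better.

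Part of the loss is an interval wider than needed. At 10% missing and correlation 0.8, the Rubin SE was 0.1082 against an empirical SE of 0.0951.

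**4. Subset membership, if imputed values were allowed to set it.** Let p be the share above 30 mg/g (assumed). A draw unrelated to the true value falls in the wrong class with probability 2p(1 − p). That is 0.42 at p = 0.70, 0.255 at 0.85 and 0.095 at 0.95. With 14 missing baselines (about 5% of 276), the subset size varies between imputations with SD √(14p(1 − p)) = 1.7, 1.3 and 0.8 patients. In a further simulation with about 80% of patients above 30 mg/g, the variance was 7%, 17% and 30% higher than with observed-baseline membership at 2%, 5% and 10% missing and correlation 0.8. At correlation 0.5 it was essentially unchanged.

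**The case against.** The strongest reply is that the tested endpoint may not be touched at all. SAP 2.1.1 and 2.5.4 define baseline as the last available value or measurement, which is naturally an observation. SAP 2.5.3 treats a derived variable as missing when a source value is missing. On that reading, everyone in the >30 mg/g subset has an observed baseline, and imputed baselines serve only the all-patients UACR analysis in Appendix D, which is outside the testing hierarchy. A reader might infer that the SAP lets an imputed value decide who is analysed; the documents do not say so. They do not exclude it either. SAP 2.4.4.2 applies baseline imputation to continuous secondary parameters without exception, and the only UACR endpoint listed in SAP 2.1.3.2 is the restricted one. What stands is an unspecified rule.

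Three other strong readings also fail:

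- **Bias.** None was seen in simulation. Baselines go missing before treatment starts, and the imputation does not use treatment.
- **Noise through the change score.** With the same baseline as covariate, the treatment coefficient and its SE are identical whether the outcome is the change or the Week 26 value. The loss comes only from a poorly predicted covariate.
- **A problem across secondary endpoints.** Screening values cover FPG, weight and SBP. For UACR, the rescheduling rule and the use of unscheduled pre-dose measurements (SAP 2.5.4) should hold the missing rate down.

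**Conclusion.** The point holds as a matter of precision and of an unstated subset rule. The baseline model uses strata alone where a better one is available. The variance cost is about 11%, 26% and 49% at 2%, 5% and 10% missing if the correlation is 0.8, and about 2%, 5% and 9% if it is 0.5. The documents give neither the correlation nor the missing rate, and the rescheduling rule points towards the low end of the missing range. The finding of no bias rests on baselines missing completely at random and complete Week 26 data.

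The cost reaches the Hochberg step only if imputed baselines enter the >30 mg/g analysis, which the SAP neither states nor prevents. This is a minor but worthwhile correction, and it does not affect the primary analysis.

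**What to change.** - State in SAP 2.4.4.2 that the UACR >30 mg/g and SBP ≥130 mmHg subsets are defined by observed baseline, with no baseline imputation for those endpoints.
- Where a baseline is still imputed, such as the all-patients UACR analysis, put treatment and the observed post-baseline values in the model together, and use the log scale for UACR. Post-baseline values without treatment could distort the comparison.
- Replace the monotone regression in this step with a method that allows a non-monotone pattern, such as fully conditional specification. Some patients will lack Week 26 but have a baseline, and others the reverse, so extending the variable list is not enough.
- Keep only the imputed baselines from that step. Discard any Week 26 values it fills in, then apply the planned endpoint imputation.
- Correct Part 2b. It creates `mi_base`, but its next steps read `ads` by imputation number, so the imputed baselines are not carried forward as written.

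**Cost.** A few patients without a baseline UACR leave the subset analysis, and there is modest extra programming. SAP 1.6 says that top-line results have been reported, so the change must be documented as made afterwards.

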2.4.4.3 Analyses of other efficacy endpoints

The analysis of other endpoints (see [Section 2.1.3](#)) will be descriptive with no formal testing. Summary statistics at scheduled visits based on observed value will be provided by each treatment group. Graphical presentations will also be used to illustrate trends over time as appropriate.

The number (%) of patients who used rescue therapy will be provided by treatment group during the 26-week core (see [Section 2.5.4](#)) and the 52-week entire double-blind treatment periods. A KM curve for the time to first rescue therapy will be presented during the 26-week core treatment period and 52-week entire treatment period (see [Section 2.5.4](#)). The list of patients who used rescue therapy will also be provided.

ESRD is defined as: (1) dialysis that persists for a duration of \geq 90 days, or positively adjudicated as ESRD if dialysis $<$ 90 days; (2) eGFR $<$ 15 ml/min/1.73 m² sustained for at least 30 days or positively adjudicated as chronic; or (3) renal transplant. The number (%) of patients with progression to ESRD at Week 4 or any time later during the study will be summarized. The same analysis will be provided during the period from the first administration of double-blind IMP (or the date of randomization if not exposed) to Week 4 (exclusive). A KM plot will be provided for time to first occurrence of ESRD up to Week 26 and the end of study respectively (see [Section 2.5.4](#)).

The number (%) of patients with >50% decline in eGFR from baseline at each scheduled visit (including Week 26 and Week 52) will be presented. The same analysis will be presented from Week 4 at each scheduled visit afterwards (including Week 26 and Week 52). A KM plot will be provided for time to first occurrence of >50% decline in eGFR from baseline up to Week 26 and the end of study respectively (see [Section 2.5.4](#)).

The number (%) of patients with UACR progression from baseline to Week 26 and Week 52, (ie, from normal to microalbuminuria or from microalbuminuria to macroalbuminuria) will be provided by treatment group respectively. A KM plot will be provided for time to UACR progression up to Week 26 and the end of study respectively (see [Section 2.5.4](#)). Similarly, the number (%) of patients with UACR improvement from baseline to Week 26 and Week 52 (from microalbuminuria to normal or from macroalbuminuria to microalbuminuria) will be provided, as well as the KM plot if appropriate.

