## **10.3 HANDLING OF PATIENT TEMPORARY OR PERMANENT TREATMENT DISCONTINUATION AND OF PATIENT STUDY DISCONTINUATION**

The IMP should be continued whenever possible. In case the IMP is stopped, it should be determined whether the stop can be made temporarily; permanent IMP discontinuation should be a last resort. Any IMP discontinuation should be fully documented in the e-CRF. In any case, the patient should remain in the study and followed for the remainder of the study to collect vital safety status and endpoint data.

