### **10.3.3 List of criteria for permanent treatment discontinuation**

The patients may withdraw from treatment with the IMP if they decide to do so, at any time and irrespective of the reason, or this may be the Investigator's decision. Patients should discuss stopping study medication with the site before doing so in order that questions can be addressed, glycemic therapy adjusted, and a follow-up assessment arranged. All efforts should be made to document the reasons for treatment discontinuation and this should be documented in the e-CRF.

The following reasons can lead to permanent discontinuation:

- At the patient's own request (ie, withdrawal of consent for treatment)
- If, in the Investigator's opinion, continuation with the administration of the study treatment would be detrimental to the patient's well-being
- Inter-current condition that requires permanent discontinuation of the study treatment as long as the abnormality persists and if the casual relationship of the concerned event and the IMP is possible (according to the Investigator's best medical judgment)
- Deterioration of renal function (defined as increase in serum creatinine >50% from baseline) that is not recovered after a temporary IMP discontinuation for 2 weeks
- Patient requires renal replacement therapy (transplant or dialysis)
- Pregnancy (in female patients)
- Specific request of the Sponsor.

Any abnormal laboratory value will be rechecked immediately to confirm the result before a decision is made to permanently discontinue IMP for the concerned patient.

For patients who prematurely discontinue the IMP, the assessments planned at EOT visit ([Section 10.1.3.2](#)) will be performed at the premature EOT Visit scheduled preferably prior to treatment discontinuation or as soon as possible after the time of discontinuation (at the latest at the next scheduled on-site visit). In the case of premature IMP discontinuation, PK samples

should not be drawn at the premature EOT visit, neither at all subsequent visits. The reason for IMP discontinuation will be clearly specified. This Premature EOT assessment may occur at a regularly scheduled visit or at an unscheduled visit.

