#### **10.3.4 Handling of patients after permanent treatment discontinuation**

Every effort should be made to maintain patients in the study. Patients should be followed up according to the study procedures as specified in this protocol up to the scheduled date of study completion, or up to recovery or stabilization of any AE to be followed up as specified in this protocol, whichever comes later.

If a patient prematurely discontinues study treatment, a premature EOT visit (see [Section 10.1.3.2](#)) should be scheduled prior to treatment discontinuation, if possible. If not possible, the Premature EOT should be scheduled as soon as possible after treatment discontinuation. In the case of early discontinuation, no sample for measuring plasma concentration should be taken at the premature EOT visit, or at any subsequent visit. For patients who discontinue treatment but remain in the study, the remaining study visits should occur as scheduled where possible. The IRT should be notified of EOT.

All cases of permanent treatment discontinuation should be recorded by the Investigator in the appropriate pages of the e-CRF.

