2.1.3 Efficacy endpoints

All efficacy measurements collected during the study will be considered for analyses, including those obtained after IMP discontinuation or introduction of rescue therapy (see [Section 2.5.4](#)).

HbA1c, FPG, UACR, UGE, urine glucose: creatinine ratio (UGCR), Cystatin C, Fructosamine, NT-proBNP and eGFR are measured/calculated in a central laboratory (see study flowchart in [Appendix E](#)). FPG, Cystatin C, Fructosamine, NT-proBNP are measured in the fasting state. Body weight, SBP and DBP (see [Section 2.1.4.5](#)) are measured at on-site visits by the investigator. Patients requiring rescue are identified as those with the reason for treatment ticked “rescue therapy” in e-CRF “Medication” page.

Efficacy variables will be summarized in both standard international units and conventional units when applicable.

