2.5 DATA HANDLING CONVENTIONS**2.5.1 General conventions**

The following formulas will be used for computation of parameters.

HbA1c

The formula to convert HbA1c from Diabetes Control and Complications Trial (DCCT) aligned value to International Federation of Clinical Chemistry and Laboratory Medicine (IFCC) standardized value is,

$$\text{IFCC-HbA1c (mmol/mol)} = [\text{DCCT-HbA1c (\%)} - 2.15] \times 10.929.$$

Renal function formulas

The estimated GFR (mL/min/1.73 m²) will be calculated using the 4 variable Modification of Diet in Renal Disease (MDRD) formula:

$$\text{Standard unit: eGFR (mL/min/1.73 m}^2\text{)} = 175 \times [\text{Serum Creatinine } (\mu\text{mol/L})/88.4]^{-1.154} \times \text{Age (year)}^{-0.203} \times 1.212 \text{ (if Black)} \times 0.742 \text{ (if female)}$$

$$\text{Conventional unit: eGFR (mL/min/1.73 m}^2\text{)} = 175 \times \text{Serum Creatinine (mg/dL)}^{-1.154} \times \text{Age (year)}^{-0.203} \times 1.212 \text{ (if Black)} \times 0.742 \text{ (if Female)}$$

UACR

$$\text{Standard unit: UACR (mg/g)} = \text{Urine Albumin (mg/dL)} / [\text{Urine Creatinine (mmol/L)} \times 11.31] \times 1000$$

$$\text{Conventional unit: UACR (mg/g)} = \text{Urine Albumin (mg/dL)} / \text{Urine Creatinine (mg/dL)} \times 1000$$

UGCR

$$\text{Standard unit: UGCR} = \text{Urine Glucose (mmol/L)} / \text{Urine Creatinine (mmol/L)}$$

$$\text{Conventional unit: UGCR} = \text{Urine Glucose (mg/dL)} / \text{Urine Creatinine (mg/dL)}$$

Calculation of LDL-C

When TG is lower than or equal to 4.52 mmol/L (400 mg/dL), LDL-C is calculated using the Friedewald equation as:

- in standard unit (mmol/L), $\text{TC} - \text{HDL-C} - \text{TG}/2.17$;
- in conventional unit (mg/dL), $\text{TC} - \text{HDL-C} - \text{TG}/5$.

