The 26-week core study period is the time from first administration of double-blind IMP to Visit 11 (Week 26) (or Day 182 if Visit 11 (Week 26) date is missing) or the end of TEAE period for the 26-week double-blind core treatment period (as defined above) whichever is later. This is for defining EOS status at Week 26.

Time to event analysis

For time to event analysis/KM plot, time to event (eg, treatment discontinuation, rescue therapy, hypoglycemia, ESRD, etc) is defined as the number of days from the date of the first administration of double-blind IMP (or the date of randomization if not exposed) to the start date of the first occurrence of the event during the respective analysis period.

Patients who did not experience any event during the respective analysis period are considered censored observations. The censoring rules are defined below.

Time to event	Censoring date at Week 26 (1st step analysis)	Censoring date at EOT/EOS (2nd step analysis)
Treatment discontinuation due to any reason	Not applicable	EOT
Treatment discontinuation due to AE	Not applicable	EOT
Time to rescue	min (EOT, Date of W26 visit)	EOT
Time to severe or documented hypoglycemia	See Section 3	Min (EOT+1, EOS)
Time to ESRD	min (EOS, Date of W26/re-allocated W26 eGFR value)	EOS
Time to eGFR decrease	min (EOS, Date of W26/re-allocated W26 eGFR value)	EOS
Time to UACR progression/improvement	min (EOS, Date of W26/re-allocated W26 UACR value)	EOS

Note: (1) Day 182 will be used if Date of Week 26 visit (or date of W26/re-allocated W26) is not available.
(2) Date of EOS will be used if date of EOT is not available; Last contact date will be used if date of EOS is not available.

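### eGFR values obtained after chronic dialysis or transplant stay in the ITT mean-change summaries and in the by-visit >50% decline count, where they can read as stable or improved kidney function

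*SAP*

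**What the plan says.** Change from baseline in eGFR and the proportion with a >50% decline are other efficacy endpoints (SAP 2.1.3.3), analysed in the ITT population (SAP Appendix D). For this group SAP 2.4.4.3 states: "Summary statistics at scheduled visits based on observed value will be provided by each treatment group". For the decline endpoint it gives "The number (%) of patients with >50% decline in eGFR from baseline at each scheduled visit", plus a Kaplan-Meier (KM) plot of time to the first such decline.

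The data rule is in SAP 2.1.3: "All efficacy measurements collected during the study will be considered for analyses, including those obtained after IMP discontinuation or introduction of rescue therapy". Under SAP 2.5.1, eGFR "will be calculated using the 4 variable Modification of Diet in Renal Disease (MDRD) formula", that is, from serum creatinine, age, race and sex.

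Protocol 10.3.3 lists the need for dialysis or transplant among the reasons for permanent discontinuation of study drug. After any such stop, Protocol 10.3 requires that "the patient should remain in the study and followed for the remainder of the study to collect vital safety status and endpoint data", and 10.3.4 says: "For patients who discontinue treatment but remain in the study, the remaining study visits should occur as scheduled where possible". The flow chart (Protocol 1.2) schedules the safety laboratory, which includes creatinine, at every post-baseline visit.

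In the censoring table of SAP 2.5.4, the row "Time to eGFR decrease" censors at end of study, or for the Week 26 version at the earlier of end of study and the Week 26 eGFR date.

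**The concern.** Once a patient is on chronic dialysis or has a graft, serum creatinine no longer reflects the native kidneys. The MDRD formula still returns a number, and the plan uses it. Two displays are exposed:

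- **Mean change in eGFR.** A transplanted patient, who has had the worst native-kidney outcome, can enter as a large improvement.
- **By-visit >50% decline.** Status is read afresh at each visit, so a patient who had met the criterion can leave the count once dialysis or a graft lowers creatinine.

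Patients enter with eGFR 15 to <30, and progression to dialysis or transplant is itself a listed endpoint, so the plan should say how the eGFR tables treat it. Otherwise one report could show an arm with more ESRD and a better eGFR mean, with no pre-specified rule to reconcile the two.

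**Working it through.** The plan states no figure on this point, so there is none to reproduce. The check has two parts: a search for a handling rule, and the SAP's own formula applied to assumed patients.

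**1. Search for a rule.** SAP 2.1.3, 2.4.4.3, 2.5.1 and 2.5.4 contain nothing that excludes, censors, imputes or counts an eGFR taken after dialysis or transplant. SAP 2.5.3 drops results that the laboratory flags as invalid, but this sits under the handling of potentially clinically significant abnormalities (PCSA) and does not address dialysis.

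**2. Formula (SAP 2.5.1).** eGFR = 175 × SCr^−1.154 × age^−0.203 for a non-Black man, with SCr in mg/dL. With age held fixed, a >50% decline needs creatinine above 2^(1/1.154) = 1.82 times baseline.

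**3. Assumed patient.** Age 65, non-Black man, baseline eGFR 20, so SCr = 3.14. His >50% threshold is eGFR below 10, or SCr above 3.14 × 1.82, about 5.73.

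**4. Dialysis (assumed start at eGFR 8, SCr 6.95, a 60% decline).** The creatinine fall that brings eGFR back to 10 is 1 − (8/10)^(1/1.154) = 17.6%.

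| Assumed fall in creatinine at sampling | eGFR recorded | Change from 20 | In by-visit >50% count? |
|---|---|---|---|
| 10% | 9.0 | −55% | yes |
| 20% | 10.3 | −48% | no |
| 30% | 12.1 | −40% | no |
| 50% | 17.8 | −11% | no |
| 65% | 26.9 | +34% | no |

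**5. Transplant (assumed graft creatinine).** SCr 1.2, 1.5 or 2.0 gives eGFR 60.8, 47.0 or 33.7, which is +204%, +135% or +68% from baseline 20.

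**6. Effect on an arm (92 planned per group, 1, 3 or 5 assumed cases).**
- Transplant, 45 recorded instead of 8: 37k/92 = 0.40, 1.21, 2.01 mL/min/1.73 m².
- Dialysis, 12 recorded instead of 5: 7k/92 = 0.08, 0.23, 0.38.
- By-visit count: k/92 = 1.1, 3.3, 5.4 percentage points lost, if each had been counted before.

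**7. Time to first decline.** The patient in step 4 is a KM event once his eGFR of 8 is recorded, and later values cannot undo that. The KM misses a patient who starts renal replacement before any >50% value is recorded. For example, baseline 16 with dialysis at an assumed eGFR of 9 is a decline of 7/16 = 44%, against a threshold below 8. He then stays at risk, event-free, to end of study. The chance of missing a fall is greater after Week 26, when visits are 13 weeks apart (Weeks 26, 39, 52) and local laboratory results do not enter efficacy analyses (SAP 2.5.4).

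**8. What exclusion does to the mean (80 observed, others at an assumed −1).**
- Three dialysis patients at 12.1 − 20 = −7.9: (77 × −1 + 3 × −7.9)/80 = −1.26. Excluding them gives −1.00, which looks better.
- One transplant at 45 − 20 = +25: (79 × −1 + 25)/80 = −0.68. Excluding it gives −1.00, which looks worse.

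Exclusion can therefore move the mean either way.

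**The case against.** The strongest reply is that the outcome is well covered elsewhere.

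- The KM is for first occurrence, so a decline already recorded is kept.
- The ESRD count and KM cover chronic dialysis, transplant and sustained eGFR <15 (SAP 2.4.4.3). From an entry-range baseline, a >50% decline means eGFR below 15, so a sustained decline is already ESRD under the SAP.
- The renal events of special interest (SAP Table 3 and 2.4.5.2) combine sustained ≥50% decrease, eGFR <15, chronic dialysis, transplant and renal death.
- The PCSA tables count a ≥50% eGFR decrease at any time in the treatment-emergent period (SAP 2.4.5.4), and the by-visit safety laboratory tables are limited to that period (SAP 2.5.4).
- Exclusion E 21 removes patients expected to need transplant or chronic dialysis, and Protocol 4.4 does not expect a high rate of clinical outcomes.
- The endpoints are descriptive, with no formal testing.

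All of this stands and limits the size of the problem. None of it corrects the ITT mean change or the by-visit count.

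Two further objections shape the remedy. Deleting values removes some of the sickest patients, so the loss must be visible. Counting renal replacement as a >50% decline would alter an endpoint that the protocol lists separately from ESRD, so it belongs beside that endpoint and should not replace it.

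A reader might infer more: that these patients vanish from the renal results, that the KM generally records them as not having declined, or that the bias always favours the arm with more renal failure. The documents support none of these. The counts above retain the patients, and the KM fails only in the case of step 7. For dialysis, the direction depends on sampling time and residual function; a 10% creatinine fall leaves the >50% flag in place.

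**Conclusion.** The gap is real and limited to two displays, plus a narrow case in the KM. As written, post-replacement eGFR enters the ITT change-from-baseline summaries and the by-visit >50% count as if it were native function. Transplant is the clear case of apparent improvement. A dialysed patient can leave the by-visit count at later visits, from a creatinine fall of about 18% in the example.

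For one to five cases in an arm of 92, the sizes are 0.4 to 2.0 mL/min/1.73 m² on the mean (transplant), 0.08 to 0.38 (dialysis), and 1.1 to 5.4 percentage points on the by-visit count. These rest on the assumed patient, the assumed creatinine values and the assumed number of cases; the documents give no expected number, and few are likely. The primary and formally tested secondary endpoints are not affected. The change is worth making because the all-values rule gives a wrong reading for these patients and the remedy is cheap.

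**What to change.** In SAP 2.4.4.3, add a rule that applies from the start date of chronic dialysis (SAP Table 3 definition) or the date of transplant:

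1. Exclude creatinine-based eGFR and cystatin C from the efficacy mean-change summaries. Show the number excluded per arm and visit, and state that this missingness is informative and can move the mean in either direction.
2. In the by-visit table and the KM, present >50% eGFR decline or chronic dialysis/transplant, with the patient counted from that date onward. Show it next to the protocol-defined >50% decline, which stays as it is.

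Dialysis and transplant are already captured on the eCRF pages named in SAP Table 3, and the ESRD KM already needs their dates, so no new data are required. The cost is one derived flag, some extra programming, and one additional row or curve.
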